## **Criteria for Early Discontinuation**

### Criteria for Early Discontinuation

A CGI-Improvement score at any time point of 6 or 7 ("much worse" or "very much worse") will trigger clinical evaluation by the study investigators, Drs. [name] or [name], for possible study discontinuation. We will assess suicidal ideation and behavior weekly from the time of consent through the completion of tDCS procedures. If individuals endorse suicidal ideation that includes a plan and intent, or have made an actual suicide attempt, research procedures will be discontinued, and open clinical treatment will be initiated immediately at an appropriate level of care.

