### **Psychological Assessments**

Psychological assessments and their timing are described in the "Assessment Instruments" section.

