### **Sample of patients with NSSI:**

Through co-enrollment in IRB #4815, participants will undergo a careful psychological assessment including characterization of DSM-IV diagnoses using the Structured Clinical Interview for DSM-IV (SCID, (First et al., 1995; First et al., 1997)). Recent suicidal ideation and behaviors will be assessed using the Columbia Suicide Severity Rating Scale (C-SSRS), which will be repeated on a weekly basis during tDCS administration to monitor emergent suicidal ideation (Posner et al., 2011). Selected items from the Self-Injurious Thoughts and Behaviors Interview (SITBI) will be used at baseline and on a weekly basis to monitor self-reported frequency, nature, motivations, and effects of NSSI, as well as urges to engage in NSSI, throughout study participation. Selected items from the Non-Suicidal Self-Injury Assessment Tool (NSSI-AT) will also be acquired at baseline to acquire additional information regarding history of NSSI behavior. The Clinical Global Impressions scale (CGI) (Guy et al., 1976) will be conducted on a weekly basis to monitor for clinical worsening. Possible mediators of treatment outcome that will be examined in the study include: emotion regulation using the Difficulties in Emotion Regulation Scale (DERS, (Gratz et al., 2004)) and the Cognitive-Attentional Syndrome Questionnaire (CAS-1; Wells, 2009); engagement with the ATT with the ATT-Scale; trait rumination with the Ruminative Responses Scale (RRS; Treynor et al., 2003) expectancy of clinical benefit, assessed with the Credibility/Expectancy Questionnaire (Devilly et al., 2000); and depression severity, as assessed by the Hamilton Depression Rating Scale (HDRS, (Hamilton, 1960)) and the Beck Depression Inventory (BDI, (Beck et al., 1961)). Tolerability of tDCS will be evaluated using the tDCS Adverse Effects Questionnaire (Aparicio et al., 2016).

Sample of remote-only patients with NSSI: Rater-administrated psychological assessments will be administered by phone or secure video-conference, and participants will be sent a link to complete self-report measures remotely through a secure platform (either REDCap, SIR, or Qualtrix). Cyberball will be remotely administered within one week before the first tDCS session and within one week after the final tDCS session. The original version of Cyberball was administered and validated for use as a digital task outside of the scanner (Williams, Cheung, & Choi, 2000).

Table: Timing of Psychological Assessments

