Assessment	Enrollment	Baseline (prior to Session 1)	Post- Final tDCS Session	Following each tDCS session	One week Post- treatment	4 week Follow -up
Credibility/Expectancy Questionnaire (CEQ)		X				
Columbia-Suicide Severity Rating Scale (C-SSRS)		X	X		X	X
Selected items from the Self- Injurious Thoughts and Behaviors Interview (SITBI)	X	X	X		X	X
Selected items from the Non- Suicidal Self-Injury Assessment Tool (NSSI-AT)	X					
Clinical Global Impressions (CGI)		X	X		X	X
Difficulties in Emotion Regulation Scale (DERS)		X	X			
Hamilton Depression Rating Scale (HAM-D)		X	X			
Beck Depression Inventory (BDI)		X	X			
tDCS Adverse Effects Questionnaire				X		
Cognitive-Attentional Syndrome Questionnaire (CAS)		X	X			
ATT-Scale				X		
Ruminative Responses Scale (RRS)		X	X			

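### The assessment timing table schedules no C-SSRS, CGI or SITBI between Baseline and the final tDCS session, although the text makes all three weekly and the course lasts 10 to about 14 days

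*Combined protocol and SAP*

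**What the plan says.** The Criteria for Early Discontinuation section, which appears twice with the same wording, commits to a frequency: "We will assess suicidal ideation and behavior weekly from the time of consent through the completion of tDCS procedures". It sets two rules. "A CGI-Improvement score at any time point of 6 or 7" leads to a clinical evaluation for possible discontinuation. Suicidal ideation with plan and intent, or an actual attempt, ends research procedures and starts open treatment.

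For timing, the Psychological Assessments paragraph under Study Procedures points elsewhere: "Psychological assessments and their timing are described in the" Assessment Instruments section. The text of that section is weekly throughout:

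- C-SSRS: "which will be repeated on a weekly basis during tDCS administration to monitor emergent suicidal ideation".
- CGI: "will be conducted on a weekly basis to monitor for clinical worsening".
- SITBI (selected items): "will be used at baseline and on a weekly basis to monitor self-reported frequency, nature, motivations, and effects of NSSI".

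The timing table in the same section has six columns: Enrollment, Baseline, post-final session, after each session, one week post-treatment and 4-week follow-up. C-SSRS and CGI are marked at Baseline, post-final, one week and 4 weeks. SITBI has those marks plus Enrollment. The after-each-session column is marked only for the Adverse Effects Questionnaire and the ATT-Scale. No column is a mid-course visit.

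**The concern.** The section that staff are sent to for timing gives two answers. Its text requires weekly ratings; its table leaves the whole treatment course without one. Nothing says which governs.

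The C-SSRS and CGI matter most, because they can bring the two discontinuation rules into play. The independent safety officer in the data and safety monitoring plan also reviews both. If the calendar is built from the table, the first scheduled C-SSRS or CGI after Baseline comes when all 12 sessions have been given. It can still lead to clinical care, but it can no longer stop stimulation. Participants currently self-injure, and the Background section describes self-injury as a strong predictor of suicide attempts.

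The SITBI is in a different position. It is weekly in the text and unmarked mid-course in the table, but neither discontinuation rule names it. Its omission loses on-treatment data on self-injury and urges; it does not remove a stopping signal.

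**Working it through.** **Inputs.** Two sessions on each of six alternating days (tDCS section); about two weeks (Background); a 7-day interval (Assessment Instruments and Criteria for Early Discontinuation); table marks as listed above. The plan's own session total reproduces: 2 × 6 = 12.

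**Step 1: length of the course.**
- Strict alternation, days 1, 3, 5, 7, 9, 11: 11 − 1 = 10 days.
- Monday-Wednesday-Friday, days 1, 3, 5, 8, 10, 12: 12 − 1 = 11 days.
- Two weeks taken literally: 14 days.

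**Step 2: interim ratings needed.** For an interval of W days with no gap above 7, the number is ceil(W/7) − 1.

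| W (days) | Needed | Marked in table |
|---|---|---|
| 10 | 2 − 1 = 1 | 0 |
| 11 | 2 − 1 = 1 | 0 |
| 14 | 2 − 1 = 1 | 0 |

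This takes Baseline as the day of Session 1.

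**Step 3: Baseline held d days before Session 1.** The interval becomes 10 + d or 14 + d.
- 10-day course: 1 rating for d = 0 to 4; 2 for d = 5 to 11.
- 14-day course: 1 rating for d = 0; 2 for d = 1 to 7.

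**Step 4: sessions after the missed point.** With Baseline on day 1, the weekly rating falls due on day 8.
- Strict alternation: days 9 and 11 remain, so 2 × 2 = 4 of 12 sessions.
- Days 1, 3, 5, 8, 10, 12, with the rating done before session 7 on day 8: days 8, 10 and 12 remain, so 3 × 2 = 6 of 12.

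**Step 5: would one fixed mid-course visit be enough?** Not always. On the 10-day course with Baseline 5 days early (day −4), a rating is due by day 3. The post-final rating on day 11 is then 11 − 3 = 8 days later. On the 14-day course with Baseline one day early (day 0), a rating is due by day 7, and the post-final rating on day 15 is again 8 days later. The added rating has to recur.

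**Step 6: consent to Baseline.** The same formula would apply, but W is not given. The C-SSRS is an eligibility instrument in the inclusion/exclusion tables. Screening runs under IRB #4815, whose schedule is not in these documents. No count can be computed.

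**The case against.** The strongest reply is that the weekly requirement is already there, more than once. The cross-reference points to the whole section, not to the table alone. The weekly text stands just before the table and the weekly suicidality rule just after it. On this view the design is sound and the table is merely incomplete. Part of that stands: the harm is conditional on staff working from the table. But the table's title says it gives the timing, and text that contradicts a schedule does not correct it.

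The second reply is that other safeguards run during treatment, and they deserve full credit. Ecological momentary assessment continues through the course with six prompts a day. It includes suicidal ideation, opens a free-text question if treatment-emergent ideation is recorded, and reminds participants of emergency contacts. There is supervised contact on six treatment days, debriefing after sessions, regular monitoring by a psychiatrist and a physician presence. The CGI trigger acts at any time point. So a reader might infer that suicidality goes unmonitored during treatment; the documents do not support that. None of these safeguards is a scheduled C-SSRS or CGI, however. No live staff review of the momentary data is described: they are downloaded on syncing, at the next visit. The debriefing is directed at discomfort, and the CGI trigger needs a CGI score to act on.

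Two further inferences should be resisted. The Research Related Delay to Treatment section allows up to 35 days before tDCS, which might suggest a fixed number of missed weekly checks before Baseline. That figure is a maximum for participants not in psychiatric treatment and is not stated to run from consent. IRB #4815 may also supply ratings. A reader might also conclude that the table is left over from a three-day course. Days 1, 3 and 5 span 4 days and would need no interim rating, and three-day wording survives in the Specific Aims and the tDCS section. No version history confirms it.

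**Conclusion.** The contradiction is real and should be fixed. Over a course of 10 to about 14 days, at least one weekly on-treatment rating each of C-SSRS, CGI and SITBI is required by the text and absent from the table. It is one if Baseline is on the day of Session 1. It becomes two if Baseline is 5 or more days earlier on a 10-day course, or 1 or more days earlier on a 14-day course. In the two calendars worked above, 4 to 6 of the 12 sessions follow the missed point.

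These counts read weekly as no more than 7 days apart. The consequence arises only if staff schedule from the table. What would then be lost is the scheduled clinician rating during treatment, not all detection. For the period from consent to Baseline the documents support a request for clarification, not a count. The on-treatment conflict does not depend on that period or on what IRB #4815 contains.

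**What to change.** Amend the timing table as follows.

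1. Add a column for weekly ratings during tDCS, marked for C-SSRS, CGI and SITBI. Ratings are no more than 7 days apart from Baseline until the post-final visit, and one of them is done before session 7, the first session of the fourth treatment day.
2. Add a footnote that the weekly suicidality check in Criteria for Early Discontinuation also applies from consent to Baseline whenever that gap exceeds 7 days. The instrument is the C-SSRS, unless IRB #4815 already provides the check.
3. Leave the any-time discontinuation trigger as it is; it should not be narrowed to scheduled visits.

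With Baseline on day 1 and strict alternation, a rating on day 7 before that day's sessions is 6 days after Baseline and 4 days before day 11. With Baseline 5 days early, ratings on days 3 and 7 give gaps of 7, 4 and 4 days.

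The cost is a table amendment and one or two short extra sets of ratings per participant during treatment, using existing instruments and staff. Any checks before Baseline depend on the wait and on IRB #4815.

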## **Background, Significance and Rationale**

### Background, Significance and Rationale

Non-suicidal self-injury (NSSI), “the deliberate, self-inflicted destruction of body tissue without suicidal intent” (Nock & Favazza, 2009), <http://www.itriples.org/issss-aboutself-i.html>, is a serious psychiatric problem (Briere & Gil, 1998; E. D. Klonsky, 2011) that is observed across a broad array of psychiatric and developmental conditions, including major depression, borderline personality disorder, intellectual disabilities, autism, Prader-Willi Syndrome, and Lesch-Nyhan Syndrome (Symons et al., 2001). NSSI is one of the most predictive risk factors for suicide attempts (Andover & Gibb, 2010; Favaro et al., 2008; E. David Klonsky, May, & Glenn, 2013; Lloyd-Richardson, Perrine, Dierker, & Kelley, 2007; Nock, Joiner, Gordon, Lloyd-Richardson, & Prinstein, 2006), and has a high prevalence, with estimates suggesting that about 21% of adult psychiatric inpatients (Briere & Gil, 1998) and 30-40% of adolescent inpatients have a history of NSSI (Darche, 1990). As the pathophysiology of NSSI is not well understood, clinicians have limited ability to predict which treatments will be most effective for specific individuals suffering from NSSI, making cases frequently persistent and treatment-refractory (Perry et al., 2009). Novel studies based on possible underlying mechanisms for NSSI are greatly needed to reduce the morbidity and mortality associated with this behavioral phenomenon.

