### Inclusion/Exclusion Criteria

Name the subject group/sub sample

Neuroimaging participants

Create or insert table to describe the inclusion criteria and methods to ascertain them

Neuroimaging participants with NSSI: Inclusion Criteria	Method of Ascertainment
1. Age 18-60	Remote interview
2. Frequent current NSSI (including cutting in which the skin is broken; self-hitting in which there is bruising; or burning in which there is evidence of a burn. Will not enroll if skin-picking or scratching is the only form of self-injury): has engaged in $\geq 2$ episodes of NSSI in the two months prior to enrollment	Remote Self Injurious Thoughts and Behaviors (SITBI) scale and remote clinical interview
3. Capacity to provide informed consent	Remote clinical interview
4. If carries a diagnosis of bipolar I or II disorder, taking or willing to begin a therapeutic dose of a mood stabilizer*	Remote SCID, remote clinical interview, therapeutic blood levels if applicable
5. Normal hearing	Remote interview
6. Physical capacity (e.g., manual dexterity) to set-up and self-administer tDCS	Remote interview

\* If not currently taking a mood stabilizer, the participant will have the option of beginning mood stabilizer with a psychiatrist on our team. We would perform any necessary blood testing to screen for appropriateness of mood stabilizer treatment and to monitor blood levels. We would provide psychiatrist visits and any necessary blood testing, but would not cover the costs of mood stabilizer medication. If participants continue to meet all other eligibility criteria upon achieving a therapeutic dose of mood stabilizer, we would proceed with research participation. If they do not, we would forego research procedures and offer 3 months of open treatment.

Create or insert table to describe the exclusion criteria and methods to ascertain them

Neuroimaging participants with NSSI: Exclusion Criteria	Method of Ascertainment
1. Unstable medical conditions based on medical history or medical assessment	Medical history (by a physician), medical assessment as conducted in IRB #4815
2. Current psychotic disorder, mania, hypomania, intellectual disability	Remote psychiatric interview and SCID
3. Dermatologic condition resulting in non-intact skin on the scalp	Medical history
4. Significant suicidal ideation with a plan and intent that cannot be managed safely as an outpatient	Remote C-SSRS, remote clinical interview

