## **Inclusion/Exclusion Criteria #4**

Name the subject group/sub sample

Remote Participants with NSSI

Create or insert table to describe the inclusion criteria and methods to ascertain them

Remote participants with NSSI: Inclusion Criteria	Method of Ascertainment
1. Age 18-60	Remote Interview
2. Frequent current NSSI (including cutting in which the skin is broken; self-hitting in which there is bruising; or burning in which there is evidence of a burn. Will not enroll if skin-picking or scratching is the only form of self-injury): has engaged in $\geq 2$ episodes of NSSI in the two months prior to enrollment	Remote Self Injurious Thoughts and Behaviors (SITBI) scale and clinical interview
3. Capacity to provide informed consent	Remote clinical interview
4. If carries a diagnosis of bipolar I or II disorder, taking a therapeutic dose or willing to begin a mood stabilizer*	Remote SCID, remote clinical interview, therapeutic blood levels if applicable
5. Normal hearing	Remote interview
6. Physical capacity (e.g., manual dexterity) to set-up and self-administer tDCS	Remote interview

\*If not currently taking a mood stabilizer, the participant will have the option of beginning mood stabilizer with a psychiatrist on our team. We would perform any necessary blood testing to screen for appropriateness of mood stabilizer treatment and to monitor blood levels. We would provide psychiatrist visits and any necessary blood testing, but would not cover the costs of mood stabilizer medication. If individuals continue to meet all other eligibility criteria once on a therapeutic dose of a mood stabilizer, we

would proceed with research procedures. If they do not, we would forego research procedures and offer three months of open treatment.

Create or insert table to describe the exclusion criteria and methods to ascertain them

Remote participants with NSSI: Exclusion Criteria	Method of Ascertainment
1. Unstable medical conditions based on medical history	Medical history and remote medical evaluation
2. Current psychotic disorder, mania, hypomania, intellectual disability	Remote psychiatric interview and SCID
3. Dermatologic condition resulting in non-intact skin on the scalp	Medical history and remote medical evaluation
4. Significant suicidal ideation with a plan and intent that cannot be managed safely as an outpatient	Remote C-SSRS and clinical interview

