### **Real-Time Monitoring of NSSI, Stressors, and Urges**

In addition to using retrospective reports of NSSI, we will also employ a recently developed assessment, Ecological Momentary Assessments (EMA). EMA records thoughts, feelings and behaviors and the circumstances preceding these experiences in real time, which may allow for a more accurate understanding of mood and behavior than retrospective reporting (Nock et al., 2009).

In this study, we will use EMA to have participants rate the frequency, duration, and severity of urges to engage in NSSI, the frequency and nature of actual NSSI, as well as suicidal ideation, relevant affects, stressors and behaviors, and possible triggers for these events, for one week prior to treatment, through the duration of the course of tDCS treatments, and one week following completion of tDCS, to measure the persistence of any observed effects. These items will be presented to each participant on an iPod device during each momentary assessment. We will enter each subject's self-reported typical waking and bedtime

---

into the software. Using this information, the program will stratify waking hours into six intervals, then randomly select one moment within each interval to deliver a prompt of an audible beep. This beep will be repeated every 30 seconds for up to 5 minutes. Collected data will be downloaded when the device is synced with a computer and can be easily imported into standard spreadsheets or statistical packages. If the participant records the presence of treatment emergent suicidal ideation, an open-ended question allowing the subject to record descriptions of their experience with this development will be presented. Subjects will also be reminded about emergency procedures to contact staff if they are concerned about suicidal ideation or risk.

We have used this procedure in a NIMH-funded study of actively suicidal patients without adverse effects and with good adherence.

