### Criteria for Early Discontinuation

A CGI-Improvement score at any time point of 6 or 7 ("much worse" or "very much worse") will trigger clinical evaluation by the study investigators, Drs. [name] or [name], for possible study discontinuation. We will assess suicidal ideation and behavior weekly from the time of consent through the completion of tDCS procedures. If individuals endorse suicidal ideation that includes a plan and intent, or have made an actual suicide attempt, research procedures will be discontinued, and open clinical treatment will be initiated immediately at an appropriate level of care.

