## **Research Related Delay to Treatment**

Will research procedures result in a delay to treatment?

Yes

Maximum duration of delay to any treatment

Study participants may continue with ongoing psychotherapeutic and/or pharmacologic treatment, as long as it was not started within 8 weeks of study enrollment. For participants not currently receiving psychiatric treatment, there may be a delay of up to 35 days prior to initiating tDCS through the study, in order to schedule baseline assessments, MRI scanning. For patients with bipolar 1 or 2 disorder not on a therapeutic dose of a mood stabilizer, evidence-based treatment with mood stabilizer treatment will be offered that would begin within 3 weeks of enrollment; tDCS research procedures would be further delayed in this case for the purposes of achieving a therapeutic dose of a mood stabilizer (prioritizing this clinical treatment ahead of research procedures).

Maximum duration of delay to standard care or treatment of known efficacy

Eight weeks

Treatment to be provided at the end of the study

One week following the conclusion of tDCS procedures, open medication-based treatment will be offered to study participants for a period of three months.

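### The suicidality stopping rule, on its more natural reading, also ends the self-injury ratings, so a participant stopped during tDCS may lose the post-treatment Aim 3 data; the expected effect is small and the remedy cheap

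*Combined protocol and SAP*

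**What the plan says.** The rule appears in the protocol section Criteria for Early Discontinuation and again, in the same words, under Assessment Instruments: "If individuals endorse suicidal ideation that includes a plan and intent, or have made an actual suicide attempt, research procedures will be discontinued". The consequence reads in full: "research procedures will be discontinued, and open clinical treatment will be initiated immediately at an appropriate level of care". Suicidality is checked weekly from consent until tDCS is complete. The same paragraph has a second trigger, a CGI-Improvement score of 6 or 7, which leads to a clinical evaluation for possible discontinuation from the study.

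The NSSI outcomes for Aim 3 come from two sources. In the table of assessment times, selected SITBI items are due at enrollment, baseline, after the final tDCS session, one week after treatment and at four weeks. EMA runs for a week before tDCS, through the course, and for "one week following completion of tDCS, to measure the persistence of any observed effects".

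The SAP analyses clinical outcomes with linear mixed effects models and EMA with mixed effects logistic regression. It defines no analysis set, gives no rule for missing data, and does not mention participants stopped for safety.

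**The concern.** Any stop during tDCS comes before every post-treatment SITBI rating and before the post-treatment EMA week. If the rule ends those ratings, the participant contributes only earlier data to the active-versus-sham comparison.

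The loss would not be haphazard. The trigger is suicidality, and the Background states that "NSSI is one of the most predictive risk factors for suicide attempts". Those whose later ratings go missing may be doing worse than their earlier ratings predict. A mixed model corrects for missingness explained by recorded ratings, but not for that excess. In a small pilot, an unequal count of one or two stops can also move the estimate, and ratings never taken cannot be recovered. A larger trial planned from this one would want to know what happened to self-injury in exactly these people.

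**Working it through.** **1. What the phrase covers.** The documents never define research procedures.

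- For the broad reading: the same paragraph uses the narrower term tDCS procedures, so a rule meant for stimulation alone could have used it. The bipolar-disorder footnotes use research procedures for participation as a whole, set against treatment: "If they do not, we would forego research procedures and offer 3 months of open treatment" (neuroimaging sample) and "If they do not, we would forego research procedures and offer three months of open treatment" (remote sample). No visible section continues SITBI or EMA after a stop.
- For a narrower reading: Research Related Delay to Treatment has "tDCS research procedures would be further delayed in this case", where the phrase is tied to stimulation. The Background places treatment after research procedures, and the Open Treatment section offers that treatment one week after tDCS, yet the four-week SITBI falls later still. On that usage the four-week rating lies outside the phrase.

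The broad reading is the more natural one, but it is not conclusive.

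**2. Inputs.** Completer targets are 22 (fMRI sample) and 24 (remote sample), from Description of Subject Population. The Lay Summary gives Aim 3 to both, and the SAP does not say whether they are pooled. The documents give no stop rate, SD, effect size or allocation ratio, so there is no planned figure to reproduce. Assumed:

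- 1:1 allocation, so 11 or 12 per arm, or 46/2 = 23 if pooled
- outcome SD 1 and true effect −0.50 SD
- correlation between ratings 0.5 to 0.7
- sham stop rate 2 to 20%

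At 2% and 10%, 22 × 0.02 = 0.44 and 22 × 0.10 = 2.2 stops are expected among 22 participants. The chance of at least one is 1 − 0.98^22 = 36% and 1 − 0.90^22 = 90%.

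**3. Same rule acting in both arms.** Simulation with 400,000 per arm and two pre-stop ratings. A participant is stopped when a score correlated r with the unrecorded later rating passes the sham threshold. The later rating is regressed on arm and pre-stop ratings among those observed, then averaged over all randomised. If stops depend only on recorded ratings, bias is about 0. Otherwise, bias toward no effect in SD at 5 / 10 / 20% stops:

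| r | correlation 0.5 | correlation 0.7 |
|---|---|---|
| 0.3 | 0.005 / 0.008 / 0.013 | 0.003 / 0.004 / 0.008 |
| 0.5 | 0.013 / 0.022 / 0.033 | 0.009 / 0.014 / 0.020 |
| 0.7 | 0.025 / 0.041 / 0.063 | 0.016 / 0.027 / 0.044 |

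At 2% stops the bias is about 0.01 SD or less. With 11 per arm the standard error is √(2/11) = 0.426 SD, and 0.063/0.426 = 0.15. A third pre-stop rating hardly changes this (maximum 0.061).

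**4. Unequal stops.** With n observed per arm, k extra stopped in one arm, and those stopped D SD worse than predicted, the difference shifts by D × k/(n + k), with standard error √(1/(n + k) + 1/n). For D = 1:

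| n | k = 1 | k = 2 |
|---|---|---|
| 11 | 1/12 = 0.083 SD (0.20 SE) | 2/13 = 0.154 SD (0.38 SE) |
| 12 | 1/13 = 0.077 SD (0.19 SE) | 2/14 = 0.143 SD (0.36 SE) |
| 23 (pooled) | 1/24 = 0.042 SD (0.14 SE) | 2/25 = 0.080 SD (0.28 SE) |

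Extra stops under active flatter tDCS, and extra stops under sham hide benefit. At D = 0.5 the shifts halve. At stop rates of 5 to 20% in step 3, stopped participants ended 0.2 to 1.1 SD above prediction, so D = 1 is near the top of the range.

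**5. Effect of early open treatment.** If it lowers post-stop ratings by an assumed 0.25 to 0.5 SD, the same formula at n = 11 gives 0.25 × 0.083 = 0.02 to 0.5 × 0.083 = 0.04 SD for one extra stop, and 0.25 × 0.154 = 0.04 to 0.5 × 0.154 = 0.08 SD for two.

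**The case against.** A reader might infer that the protocol orders outcome ratings to stop. It does not say so. Its paragraph separates discontinuing research procedures from possible discontinuation from the study, and the bipolar footnotes concern people found ineligible before research begins, not follow-up of randomised participants. Consent pages are not in the reviewed text and could describe later data collection. All of this stands, so the finding rests on the more natural reading of an undefined term. It does not remove the gap, because staff managing a suicidal participant could read the rule either way.

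High stop rates are also doubtful. Both recruiting samples exclude a suicide attempt or a hospitalisation for serious self-harm in the past three months, and plan-and-intent ideation that cannot be managed as an outpatient. The tDCS course lasts about two weeks. For participants not in treatment, tDCS may start up to 35 days after entry, and a stop before randomisation costs the comparison nothing. The 20% rate behind the largest bias is therefore an upper bound with no support in the documents. The figure of 11 or 12 per arm is likewise an assumption, and pooling roughly halves the unequal-stop shifts. These points stand.

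Finally, using ratings regardless of open treatment is a choice of estimand that the documents do not make. If the sponsor wants the effect without early rescue treatment, leaving out post-stop ratings under a likelihood model is defensible. By step 5, open treatment could move the estimate by about as much as the bias being removed. This is a reason to report both analyses, not to leave the ratings uncollected.

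**Conclusion.** The concern holds in a limited form. On its more natural reading the rule may cost a participant stopped during tDCS all post-treatment NSSI ratings, for a reason plausibly tied to the outcome, and the SAP has no provision for it.

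It would be wrong to conclude that Aim 3 is seriously biased or that stopped participants drop out of the analysis. Their earlier ratings remain usable in the mixed models, and the systematic bias is about 0 to 0.06 SD over stop rates of 2 to 20%. Its maximum is about 5% of the effect detectable with 80% power at 11 per arm: (1.96 + 0.84) × 0.426 = 1.19 SD, and 0.063/1.19 = 0.05. The shifts of 0.08 and 0.15 SD (0.04 and 0.08 SD pooled) reflect chance imbalance combined with a 1 SD departure, and are not expected bias. All sizes rest on the stated assumptions and a single normal outcome; the effect on EMA, analysed by logistic regression, is not quantified.

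The case for acting is that the missing ratings are irrecoverable and cheap to keep. Label: cheap improvement, low priority.

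**What to change.** **Protocol, both copies of Criteria for Early Discontinuation.** State that tDCS, MRI and Cyberball are discontinued, leaving triggers and clinical care unchanged. Add that SITBI, C-SSRS and CGI continue by phone or video at the planned post-final, one-week and four-week times, with EMA only if the clinician agrees, unless consent is withdrawn or the clinician judges it unsafe. Record the dates of the stop and of the start of open treatment.

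**SAP.** Keep all randomised participants in the Aim 3 models. Report the result both with and without ratings taken after early open treatment, meaning treatment begun before the one-week point at which everyone is offered it. The sponsor should name in advance which is the main analysis.

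**What it buys.** In the step 3 setting at 20% stops, with ratings used regardless of open treatment, bias falls from about 0.06 SD to under 0.01 SD if 80% of stopped participants are reached, and to about 0.02 SD if half are. Both reach rates are assumed.

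**Cost.** An amendment needing IRB approval, and up to three short contacts per stopped participant. The instruments are already scheduled, the phone and video route is already used for remote participants, and the four-week SITBI already falls after open treatment is offered. Some ratings will reflect open or acute care, and some participants, such as those admitted, may not be reachable.
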